5.4.7. Pharmacokinetic Assessment

Serum LY2951742 concentration will be determined in trial participants following LY2951742 administration at specified visits throughout the trial. Pharmacokinetic assessments will be summarized in the PK/PD analysis plan.

5.5. Statistical Analyses

The SAP Version 1 will be approved prior to first patient visit and any unblinding of the study team. The SAP Version 1 supersedes the statistical plans described in the protocol.

5.5.1. General Considerations

Treatment effects will be evaluated based on an overall one-sided significance level of 0.025 for all efficacy and safety analyses. Ninety-five percent confidence intervals (CIs) for the difference in least-square means (LSMeans) between treatment groups will be provided.

Change from baseline of continuous variables with repeated measures will be analyzed using a mixed model repeated measures (MMRM) analysis. An MMRM analysis refers to a restricted maximum likelihood (REML)-based, mixed-effects repeated measures analysis using all the longitudinal observations at each post-baseline visit. Additionally, an analysis of variance (ANOVA) or an analysis of covariance (ANCOVA) model will also be used to analyze the change from baseline to the average monthly measures during 6-month treatment phase (for measures with corresponding objectives evaluated over the 6-month treatment period), or to last observation carried forward (LOCF) endpoint (for measures with corresponding objectives evaluated at Month 6).

For other continuous variables, the change from baseline to LOCF endpoint will be analyzed using an ANOVA or ANCOVA model.

Unless otherwise specified, when an ANOVA model or ANCOVA model is used to analyze a continuous efficacy variable, type III sum-of-squares for the LSMeans will be used for the statistical comparisons.

Binary variables with repeated measures will be analyzed in a generalized linear mixed models (GLIMMIX) as pseudo-likelihood-based mixed effects repeated measures analysis.

For categorical efficacy variables without repeated measures, comparisons between treatment groups will be performed using logistic regressions to adjust for more covariates (see Section 5.5.1.1 for details). For other categorical variables without repeated measures, comparisons between treatment groups will be performed using Fisher's exact tests. Unless specified otherwise, Fisher's exact test will be used for comparisons of baseline measures (eg, baseline patient characteristics, previous therapy, etc.) and categorical safety measures; logistic regression will be used for comparisons of post-baseline efficacy measures.

For details of analysis methods, please refer to the following sub-sections.

Any change to the data analysis methods described in the protocol will require an amendment ONLY if it changes a principal feature of the protocol. Any other change to the data analysis methods described in the protocol, and the justification for making the changes, will be described in the statistical analysis plan and/or in the clinical study report.

Additional exploratory analyses of the data will be conducted as deemed appropriate.

Statistical analysis of this study will be the responsibility of Eli Lilly and Company or designee. SAS[®] software will be used to perform most or all statistical analyses.

Comparisons between LY2951742 and Placebo refer to comparison of each LY2951742 arm with Placebo.

5.5.1.1. Adjustments for Covariates

The MMRM models will include the fixed, categorical effects of treatment, pooled region1, month, and treatment-by-month interaction, as well as the continuous, fixed covariates of baseline value and baseline-by-month interaction. The baseline value and baseline-by-month interaction are included to account for the differential influence over time that the baseline value has on the post-baseline values. Pooled region1 is defined in Section 5.5.1.3. Pooled region1 will be excluded from MMRM models for safety measures.

When an ANOVA model is used to analyze a continuous efficacy variable at the LOCF endpoint, the model will contain the main effects of treatment and pooled region1. When an ANCOVA model is used to analyze a continuous efficacy at the LOCF endpoint, the model will contain the main effects of treatment and pooled region1 and appropriate baseline value as a covariate. When an ANOVA or ANCOVA model is used to analyze a continuous safety variable, the pooled region1 will be removed from the model.

The GLIMMIX models for the repeated binary outcomes will include the fixed, categorical effects of treatment, month, and treatment-by-month interaction, as well as the continuous, fixed covariate of baseline value. Pooled region1 and the baseline value-by-month interaction will be excluded from the model in order to increase the likelihood of convergence.

When a logistic regression is used to analyze a binary variable, the model will include the main effect of treatment, pooled region1 (if appropriate), and appropriate baseline value as a covariate. Pooled region1 may be excluded from the model in case of non-convergence.

With the exception of efficacy analyses on migraine headache days or categorical analysis of response rate (such as 50% response rate) derived from migraine headache days where the continuous value of baseline migraine headache days will be used as covariate, all other efficacy analyses will include baseline number of migraine headache days category (<8 vs ≥8) as a covariate in the MMRM, AN(C)OVA, GLIMMIX and logistic regression model. Specifically, for time to event analysis of 50% response (such as Time to first 50% response in double-blind treatment phase and Time to first loss of 50% response in post-treatment phase), stratified log rank test will be used with the baseline number of migraine headache days category (<8 vs ≥8) as 1 of the covariates

5.5.1.2. Handling of Dropouts or Missing Data

Two statistical approaches to handling missing data will be used as appropriate: repeated measures analyses and ANCOVA/ANOVA model using change from baseline to the average of observed monthly values during 6 months of treatment phase (for measures with objectives evaluated during the entire 6 months of treatment phase), or change from baseline to LOCF endpoint (for measures with objectives evaluated at Month 6).

For the repeated measures analyses, the model parameters are simultaneously estimated using restricted likelihood estimation incorporating all of the observed data. Estimates have been shown to be unbiased when the missing data are missing at random.

Please refer to Section 5.4.1 for approach to handling missing diary data for derivation of the number of migraine headache days and other efficacy measures (with the exception of migraine attacks) derived from ePRO data per 30-day period.

Approaches to Handling Missing Diary Data for the Derivation of Migraine Attack

For the analysis of migraine attack, the LOCF method will be used to impute the missing ePRO diary days. In other words, if the patient was migraine headache free on the day before the missing ePRO diary day, this would be carried forward as no migraine headache day until the actual next non-missing diary day. On the other hand, if the day before the missing diary day is a migraine headache day, then it would be carried forward as migraine headache day until the next non-missing diary day. The imputation will be carried out for all the missing diary days between the first non-missing to the last day during that period.

If the compliance rate for a monthly interval is $\leq 50\%$, the number of migraine attacks during that month will be considered missing. Please refer to Section 5.4.1 for compliance rate calculation.

5.5.1.3. Definition of Geographic Regions

In CGAG, eligible patients will be randomized within each of the following 4 regions: United States (US) east, US west, Puerto Rico, and Canada. In CGAH (which includes additional countries from European Union (EU) and other regions), eligible patients will be randomized within each country.

In CGAH and integrated efficacy analysis, subgroup analyses for primary measure will be done by a subgroup variable of region defined below:

- North America, including the US;
- Europe, including United Kingdom (UK), Netherlands, Spain, Czech, and Germany;
- Other, including Argentina, Israel, Korea, Taiwan, and Mexico

In order to clarify the different definitions of regions and be consistent for CGAG and CGAH, 2 variables of regions are defined. Region1 is the smallest geographic area within which the randomization is done. Region2 is a larger geographic area which defines the subgroup variable of region. The definitions are summarized in Table 5.4 below.

All regions in region1 (as defined in Table 5.4 below) with fewer than 2 randomized patients per LY-treated group or fewer than 4 randomized patients in placebo group with nonmissing baseline and at least 1 post-baseline values of the number of migraine headache days will be pooled.

All analyses will use pooled region1, unless otherwise specified.

Variable Name	Definition in CGAG	Definition in CGAH
Region1 (Randomization Region)	US eastUS westCanadaPuerto Rico	• Country
Region2 (Subgroup Region)	NA* (all from one region, ie, North America, including the US and Canada)	 North America, including the US; Europe, including UK, Netherlands, Spain, Czech, and Germany; Other, including Argentina, Israel, Korea, Taiwan, and Mexico

Table 5.4. Definition of Region1 and Region2

5.5.1.4. Analysis Populations

There were 3 analysis populations defined:

- **Intent-to-Treat (ITT) Population**: All patients who are randomized and received at least one dose of study drug.
- **Safety Population**: This population is the same as the ITT population defined above.
- **Post-treatment Population**: All patients who entered the post-treatment phase (Study Period IV) as indicated by entering any post-treatment visit (telephone or office visit). Analyses of Study Period IV only (that is, excluding Study Period III) will be based on the post-treatment population.

Unless otherwise specified, all analyses will be conducted according to the ITT principle on the ITT population. That is, patients will be analyzed according to the treatment they were randomized to, regardless of whether they actually received a different treatment.

Safety analyses (in Section 5.5.12), as well as analyses for disposition and exposure, will be conducted based on the modal treatment the patient received during the double-blind treatment period. For determining modal treatment, do not consider the loading dose visit for patients assigned to an LY120-mg treatment group, but do consider it for patients assigned to the placebo and LY240-mg treatment groups. If there are 2 or more modes, then add the loading dose visit and recalculate the mode. If there is still a tie, the highest dose of the modes is to be used.

5.5.1.5. Baseline and Post-Baseline Definition

Table 5.5 describes the rules for determining the patient population and baseline and post-baseline observations for each study phase and type of analysis. When "last of Visit x-x" is used in the table, the last nonmissing observation obtained in the visit interval will be used.

^{*}No subgroup analysis by region2 for CGAG since all patients will be from North America.

Table 5.5. Patient Population with Baseline and Post-Baseline Definitions by Study Period and Type of Analysis

Study Period/Analysis	Patient Population	Baseline Observation	Post-baseline Observation(s)
Study Period III			
Primary/secondary/exploratory efficacy analyses (repeated measures or average of observed monthly values)	ITT population with a baseline and at least one post-baseline observation	Visit 3	All scheduled visits 3 <visits<=12< td=""></visits<=12<>
Primary/secondary/exploratory efficacy analyses at LOCF endpoint	ITT population with a baseline and at least one post-baseline observation	Visit 3	Last of Visit 3.01- 12
Quality of Life analyses (repeated measures)	ITT population with a baseline and at least one post-baseline observation	Visit 3	All scheduled visits 3 <visits<=12< td=""></visits<=12<>
Quality of Life analyses at LOCF endpoint or for average of observed monthly values	ITT population with a baseline and at least one post-baseline observation	Visit 3	Last of Visit 3.01- 12
TEAEs	Safety population	All Visits 1-3	All Visits 3.01-12
Serious adverse events, discontinuations due to adverse events	Safety population	NA	All Visits 3.01-12
C-SSRS categorical analyses	Safety population with a baseline and at least one post-baseline C-SSRS assessment	Recent history: All Visits 1-3 excluding lifetime ^a All prior history: Visits 1-3 including lifetime ^a	All Visits 3.01-12
Treatment emergent abnormal laboratory values	Safety population with normal laboratory values at all nonmissing baseline visits (with respect to direction being analyzed) and who have at least one post-baseline observation	Low: Minimum value from Visits 1-3 High: Maximum value from Visits 1-3	Low: Minimum value from Visits 3.01-12 High: Maximum value from Visits 3.01-12
Treatment emergent immunogenicity	Safety population	Visit 3	All Visits 3.01-12
Treatment emergent changes in temperature and weight	Safety population with a baseline and at least one post-baseline observation	Low: Minimum value from Visits 1-3 High: Maximum value from Visits 1-3	Low: Minimum value from Visits 3.01-12 High: Maximum value from Visits 3.01-12

Patient Population with Baseline and Post-Baseline Definitions by Study Period and Type of Analysis

			Post-baseline		
Study Period/Analysis	Patient Population	Baseline Observation	Observation(s)		
Study Period III					
Treatment emergent changes in blood pressure, pulse, and ECGs	Safety population with a baseline and at least one post-baseline observation	Low: Last non-missing from Visits 1-3 High: Last non-missing from Visits 1-3	Low: Minimum value from Visits 3.01-12 High: Maximum value from Visits 3.01-12		
Continuous safety analyses (repeated measures)	Safety population with a baseline and at least one post- baseline observation	Last of Visits 1-3	All scheduled visits 3 <visits<=12< td=""></visits<=12<>		
Continuous safety analyses—change from baseline to LOCF endpoint (ANCOVA)	Safety population with a baseline and at least one post-baseline observation	Last of Visits 1-3	Last of Visits 3.01-12		
Study Period III and IV combined					
Primary/secondary/exploratory efficacy analyses	ITT population with a baseline and at least one post-baseline observation	Visit 3	All scheduled visits 3 <visits≤14< td=""></visits≤14<>		
Quality of Life analyses	ITT population with a baseline and at least one post-baseline observation	Visit 3	All scheduled visits 3 <visits≤14< td=""></visits≤14<>		
Continuous safety analyses (repeated measures)	Safety population with a baseline and at least one post-baseline observation	Visit 3	All scheduled visits 3 <visits≤14< td=""></visits≤14<>		
Treatment-emergent immunogenicity	Safety population	Visit 3	All Visits 3.01-14		
Study Period IV					
Post-treatment–emergent adverse events	Post-treatment population	All Visits 1-12	All Visits 12.01-14		
Serious adverse events, discontinuations due to adverse events	Post-treatment population	NA	All Visits 12.01-14		
Post-treatment–emergent abnormal laboratory values	Post-treatment population with normal laboratory values at all nonmissing baseline visits (with respect to direction being analyzed) and who have at least one post-baseline observation	Low: Minimum value from Visits 1-12 High: Maximum value from Visits 1-12	Low: Minimum value from Visits 12.01-14 High: Maximum value from Visits 12.01-14		
Treatment-emergent immunogenicity	Post-treatment population	Visit 3	All Visits 12.01-14		

Patient Population with Baseline and Post-Baseline Definitions by Study Period and Type of Analysis

Study Period/Analysis	Patient Population	Baseline Observation	Post-baseline Observation(s)
Study Period IV			
Treatment-emergent changes in	Post-treatment population with a baseline and at least one	Low:	Low:
temperature and weight	post-baseline observation	Minimum value from	Minimum value from
		Visits 1-12	Visits 12.01-14
		High:	High:
		Maximum value from	Maximum value from
		Visits 1-12	Visits 12.01-14
Treatment-emergent changes in blood	Post-treatment population with a baseline and at least one	Low:	Low:
pressure, pulse and ECGs	post-baseline observation	Last non-missing from	Minimum value from
		Visits 1-12	Visits 12.01-14
		High:	High:
		Last non-missing from	Maximum value from
		Visits 1-12	Visits 12.01-14

Abbreviations: ANCOVA = analysis of covariance; C-SSRS = Columbia Suicide Severity Rating Scale; ECG = electrocardiogram; ITT = intent-to-treat; LOCF = last observation carried forward; NA = not applicable; TEAE = treatment-emergent adverse event.

Note: Visit 3.01 indicates the first unscheduled visit occurring after Visit 3 and prior to Visit 4. Visit 12.01 indicates the first unscheduled visit occurring after Visit 12 and prior to Visit 13.

^a Lifetime is captured in the C-SSRS visit 1 CRF.

5.5.2. Patient Disposition

The number and percentage of ITT patients who complete the study or discontinue early will be tabulated for all treatment groups for Study Period III and Study Period IV both overall and by visit. Reasons for discontinuation will be compared between treatment groups using Fisher's exact test for Study Period III with the ITT population. Descriptive statistics only will be presented for the treatment groups in Study Period IV with post-treatment population. Subcategories of discontinuation due to subject decision will be summarized too.

Patient allocation by investigator will be summarized for Study Period III for all ITT patients.

Patient allocation by investigator will also be listed for all study periods.

5.5.3. Important Protocol Deviations

Important protocol deviations that potentially compromise the data integrity and patients' safety will be summarized by treatment group for all intent-to-treat population.

Section 7 (Appendix) contains a table that lists the categories, subcategories, and study-specific terms of important protocol deviations, source of identification, and the method to identify each deviation. Per study team's discretion, for non-programmable protocol deviations, additional categories and subcategories other than the ones in Appendix Table 1 can always be added into the final non-programmable protocol deviations list, as deemed necessary.

A table and listing of important protocol deviations for Intent-to-Treat patients during baseline, double-blind treatment phase, or post-treatment phase, will be provided by each randomized treatment arm and overall.

5.5.4. Patient Characteristics

The following patient characteristics at baseline will be summarized by treatment group for all ITT patients.

- Demographic (age, gender, ethnic origin, height, weight, body mass index)
- Migraine and/or headache measures per 30-day baseline period.
 - o number of migraine headache days
 - o number of migraine headache days with abortive (acute) medication use
 - o number of migraine headache hours
 - o number of migraine attacks
 - o number of headache days
 - o number of moderate-severe headache days
 - o number of headache hours
 - o number of ICHD migraine headache days

- mean severity of migraine headaches
- o number of migraine headache days with aura
- o number of migraine headache days with nausea and/or vomiting
- o number of migraine headache days with photophobia and phonophobia
- o number of migraine headache days with prodromal symptoms other than aura
- Had migraine with Aura at baseline
- o Prior migraine preventive treatment:
 - Without prior migraine preventive treatment
 - With prior migraine preventive treatment and did not fail
 - With prior migraine preventive treatment and failed at least 1 medication
 - With prior migraine preventive treatment and failed at least 2 medications.
 - Number of prior migraine treatment failed: 1, 2, 3, ...
- o Baseline number of migraine headache day category (≤ 8 versus ≥ 8)
- PGI-S
- Alcohol, tobacco, caffeine and nicotine consumption
- Medical history and Pre-existing condition

Comparisons between treatment groups will be performed using Fisher's exact test for categorical data and ANOVA with treatment as independent variables in the model for continuous data.

Medical history and pre-existing conditions will be summarized by preferred term (PT) within system organ class (SOC), and comparison between treatment groups will be performed using Fisher's exact test. Medical history is defined as illness(es) that ended prior to the signing of informed consent. Pre-existing conditions and AEs at baseline are those AEs occurring during the baseline/screening visits for the study period, that is, Visit 1, 2, and 3.

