**Study Period III**: At the start of the 6-month double-blind treatment phase (Visit 3), patients meeting all eligibility requirements will be randomized to 1 of 3 treatment groups in a 2:1:1 ratio to receive placebo, 120 mg/month LY2951742, or 240 mg/month LY2951742, respectively.

Patients randomized to the 120 mg dose of LY2951742 will receive an initial loading dose of 240 mg (2 injections of 120 mg each at Visit 3 only). To preserve blinding throughout the study, patients in all treatment groups will receive 2 injections of investigational product at each dosing visit (two placebo injections, two 120-mg LY2951742 injections, or one placebo injection and one 120-mg injection). At Visit 3, if available and where local regulations and Ethical Review Boards allow, patients will also watch a training video designed to address patient expectations with regard to participation in a placebo-controlled trial and the difference between medical treatment and research.

The patient will be considered enrolled in the study when randomization occurs. During this phase, study procedures at dosing visits must always occur prior to the patient receiving their assigned treatment.

Patients will be given injections of investigational product during office visits (Figure CGAH.1). For all treatment groups, subcutaneous injections will be administered once monthly at the dosing visits. At Visit 3 (first dose), patients will be required to remain in the office for observation for 30 minutes post injection. Patients will continue to log in and complete the ePRO diary each day. Patients may continue to take their allowed acute migraine headache medication (with some limitations; see Section 6.8) during the treatment phase.

Patients who complete this phase or discontinue for any reason during Study Period III will be expected to enter post-treatment follow-up (Study Period IV).

**Study Period IV**: During this 4-month phase, sites and patients will remain blinded to patients' treatment assignments. Patients will follow all study procedures during Study Period IV but will not receive LY2951742 or placebo. One month after Visit 12, if clinically warranted due to a worsening of symptoms, patients may start migraine prevention medications at the discretion of

the investigator. The list of allowed preventive medications is provided in Section 6.8. At Visit 14 (Month 10), patients will return to the site for their last study visit and discharge from the study.

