5.5.5. Exposure to Investigational Product

Patients will receive the investigational medicinal product (IMP) at the following planned time points:

- Beginning of Month 1 (Visit 3)
- Beginning of Month 2 (Visit 5)
- Beginning of Month 3 (Visit 6)

- Beginning of Month 4 (Visit 7)
- Beginning of Month 5 (Visit 8)
- Beginning of Month 6 (Visit 10)

The following information will be recorded on the eCRF for each dose:

- Confirmation that the patient received the IMP (including reason if the IMP was not given)
- Date and time of administration

The following will be derived from the information recorded on the eCRF:

- For treatment phase (SP III), duration of exposure in days is calculated as treatment phase disposition date first date IMP administered +1.
- For treatment phase (SP III), number and percentage of patients with 1, 2 and 3, 4, 5, or 6 doses injected.

Comparisons between treatments for duration of IMP exposure will be performed using an ANOVA with treatment in the model. Number of patients with 1 dose, 2, 3, 4, 5 or 6 doses injected will be compared between treatment groups with Fisher's exact test.

In addition, injections not administered will be listed.

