5.5.12. Safety Analyses

The safety analyses will be conducted for Study Period III, Study Period IV, as well as Study Periods III and IV combined.

For Study Period III and Study Period IV separately, the safety analyses outlined in the following sub-sections will be conducted.

For Study Period III and IV combined, only the change from baseline with MMRM analysis (Section 5.5.10.1) will be conducted.

The safety and tolerability of treatment will be assessed by summarizing the following:

- TEAEs
 - o By PT by decreasing frequency
 - o By SOC

- o By maximum severity
- o By High Level term
- o By considered to be related to investigational produce by investigator
- SAEs
- AEs leading to discontinuation
- Suicide-Related Thoughts and Behaviors
- Vital signs and weight
- Laboratory measurements
- ECGs
- Antibodies (ADA and NAb)

The baseline and post-baseline for all safety measures are described in Table 5.5 unless specified otherwise.

As summarized in CGAG protocol addendum 2 (CGAH Protocol Addendum 7), to characterize the time course of treatment-emergent ADA, additional data will be collected after patients completed or discontinued from study. Individual patient listings of those data including concomitant medication, adverse events and ADA measurements will be created.

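### Does the SAP turn a reaction that starts on site after the first injection into a baseline adverse event?

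*SAP*

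**What the plan says.** SAP 5.5.12 makes one table the authority for safety windows: "The baseline and post-baseline for all safety measures are described in Table 5.5 unless specified otherwise". In the Study Period III part of Table 5.5, the TEAE row takes Visits 1 to 3 as baseline and "All Visits 3.01-12" as post-baseline. The row for serious adverse events (SAEs) and discontinuations due to adverse events has the same post-baseline window and no baseline. The table note explains that "Visit 3.01 indicates the first unscheduled visit occurring after Visit 3 and prior to Visit 4". In its list of baseline characteristics, SAP 5.5.4 adds that "AEs at baseline are those AEs occurring during the baseline/screening visits for the study period, that is, Visit 1, 2, and 3".

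Dose 1 is given at Visit 3 (SAP 5.5.5). Protocol 4.1 states: "At Visit 3 (first dose), patients will be required to remain in the office for observation for 30 minutes post injection". The same section says that "study procedures at dosing visits must always occur prior to the patient receiving their assigned treatment".

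SAP 5.5.12.1.1 defines TEAEs by phase: an event counts if it is new, or worse than the highest baseline severity for the same MedDRA Lowest Level Term (LLT). SAP 5.5.12.1.1.1 and 5.5.12.1.1.2 then tabulate treatment-emergent hypersensitivity and injection-site events by time since dosing. The first category is under 60 minutes.

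**The concern.** Visit 3 straddles the start of treatment, and the adverse event rows do not say where it divides. If all of Visit 3 is baseline, a reaction ten minutes after the first injection is classed as existing before treatment. Three things would follow:

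- The event is lost as a TEAE and cannot enter the under-60-minute category.
- It sets the baseline severity for its LLT, so a reaction of equal severity after a later dose is not treatment-emergent either.
- An SAE or a discontinuation event starting in that interval falls outside the window for its row.

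Immediate hypersensitivity and injection-site reactions are named safety topics here. Visit 3 is also the only visit at which the 120 mg arm receives two active injections. Two programmers working from the same table could report different counts.

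**Working it through.** No sample size, error rate or event rate is involved. The check sets the passages side by side, applies them to a test case and measures the width of the gap.

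**1. Can the visit labels be taken word for word?** No. Most adverse events start between visits. An event starting at home on day 10 occurs during no visit, so a strict reading would leave it in neither window. The rows must be read either as intervals (phases) or as the visit at which the event is collected.

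**2. Read as phases.** Protocol 4.1 places the start of the double-blind treatment phase at Visit 3. Protocol 5.1, criterion 4, runs the prospective baseline from Visit 2 to Visit 3. The TEAE definition compares the post-baseline phase with the baseline phase. An event after the injection belongs to the treatment phase.

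**3. Read as collection visit.** The column headings of Table 5.5 refer to observations. The Schedule of Activities (Protocol Appendix 2) has adverse events collected at Visit 3, and its footnote k puts the injection after all other procedures. The scheduled Visit 3 collection is therefore pre-dose. A reaction after dosing is picked up at an unscheduled 3.01 visit or at Visit 4, where spontaneously reported events are reviewed. Both are post-baseline.

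**4. The SAP's own gloss on the same windows.** The suicidality row of Table 5.5 also uses Visits 1 to 3 and 3.01 to 12. SAP 5.5.12.1.2 describes the first as prior to treatment and the second as during treatment. For blood pressure, pulse and ECG, SAP 5.5.12.1.3 and 5.5.12.1.4 end the baseline before randomization.

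**5. The under-60-minute category.** It applies to every dose, so doses 2 to 6 can fill it under any reading, and nothing in it contradicts Table 5.5. It does show that the authors meant immediate post-dose events to count as treatment-emergent.

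**6. Test case:** a mild injection-site reaction 10 minutes after dose 1, with the same LLT at the same severity after later doses.

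| Rule | Dose 1 event | Later events | Patients with the TEAE | Dosing visits able to supply on-site TEAEs |
|---|---|---|---|---|
| All of Visit 3 is baseline | baseline | not worse than baseline | 0 | 5 of 6 (Visits 5, 6, 7, 8, 10) |
| Split at first injection | TEAE | TEAE | 1 | 6 of 6 (adds Visit 3) |

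The 0-versus-1 difference needs on-site onset, an identical LLT and no later worsening.

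**7. Width of the interval.**
- Scheduled treatment phase, Visit 3 to Visit 12: 14 + 16 + 30 + 30 + 30 + 15 + 15 + 15 + 15 = 180 days, and 180 × 24 = 4,320 hours.
- Minimum on-site stay: 0.5 / 4,320 = 0.012% of that time.
- Under-60-minute windows over six doses: 6 × 60 = 360 minutes. The stay covers 30 / 360 = 8.3%, or 60 / 360 = 16.7% if the patient stays a full hour.

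These are shares of time. They show how narrow the gap is and do not estimate events or bias.

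**8. Is there a second gap?** The Study Period IV rows use "All Visits 12.01-14", so Visit 12 has the same form of boundary. The last dose is at Visit 10, so no post-dose interval is at issue there.

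**The case for a change.** The best case for a change is that none of these sentences states the cut-point for adverse events. Rules on the order of procedures do not assign a phase to an event that begins during post-dose observation. SAP 5.5.4 speaks of events occurring at the visit, not of events reported there, and the deviation table in SAP Section 7 treats the 30-minute observation as part of the randomization visit. The SAP fixes the boundary elsewhere: before randomization for vital signs and ECG, by date of first injection for previous preventive therapy (5.5.8), and by a same-day rule for concomitant medication (5.5.9). Adverse events, where onset relative to injection matters most, have no such rule. The dose time is already recorded, so a sentence would cost little.

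Part of this stands. The cut-point is unwritten. The documents also do not say whether onset time is collected for every adverse event, so some Visit 3-date events may need a convention.

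The step from there to a misclassification does not stand. SAP 5.5.4 describes the baseline characteristics tables and is not the TEAE algorithm. The argument needs an interval reading for every event except those in the minutes after dose 1, and a word-for-word reading for those. Other outputs would also show much of what might be lost: hypersensitivity listings give timing relative to the last dose, the registry summary in SAP 5.9 counts SAEs whether or not they are treatment-emergent, and SAP 5.5.2 compares reasons for discontinuation over Study Period III.

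**Conclusion.** No change is needed. The SAP leaves a detail unwritten, and the rest of the plan fills it in one direction: baseline ends, and the treatment-emergent window opens, at the first injection. An analyst who read all of Visit 3 as baseline would have to set aside the phase-based TEAE definition, the order of procedures at dosing visits, the SAP's gloss on the same windows for suicidality, and the purpose of the under-60-minute category.

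Even on the unfavourable reading, the exposure is one of six dosing visits and at least 30 minutes out of 4,320 hours. It is limited to TEAE, SAE and discontinuation counts for events starting in that interval. All three arms receive two injections and the same observation, so the interval exists in every arm; the size and between-arm direction of any effect are unknown. No primary or key secondary inference is touched.

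The conclusion assumes that programming follows phase or collection visit, as the documents imply, and that onset relative to dosing can be recovered where it matters. The second assumption is well supported for the two named topics: the date and time of each dose are recorded, and the eCRF captures event timing for hypersensitivity and injection-site events.
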